**After enrollment is complete, parents/guardians of study participants will take part in the following study procedures:**

**Figure 2. Outline of Study Procedures**

**Weekly Check-in Survey:** Parents of enrolled students will be asked to complete an online weekly 5-minute survey throughout the duration of the study that asks if their child is experiencing symptoms consistent with COVID-19 and has sought health care, if they have been absent from school in the past week, or if they have been exposed to someone with suspected COVID-19. Parents will also be asked if their child has been tested for SARS-CoV-2 at the Yakima School district static test site.

**Secondary Outcome Assessments:** Participants will be asked to participate in secondary outcome assessment surveys for the index child in each family collected either online, on paper, or by phone, based on their preferences. The index child will be selected based on the child with the most recent birthday from the time of enrollment if there is more than one child enrolled in a family. The goal is to conduct 900 secondary outcome assessments: 450 parents of children in the intervention group and 450 parents of children in the control group. Study surveys are available in both English and Spanish, as chosen by the participating parent or guardian.

Parents will be asked to complete surveys on topics such as their own and their child's perceived stress, sleep disturbance, physical activity, and emotional regulation (including both depressive and anxiety symptoms). Secondary outcome survey assessments will be offered to participants to be completed at the time of enrollment, halfway through the study (month 4), and at the end of the study (month 6). In order to better understand potential moderators and mediators of intervention effects, these surveys will also assess health literacy (at enrollment only), positive and negative outcomes expectations around testing and vaccines, and self-efficacy around testing, mask use, discussing COVID-19 with a healthcare provider and risk communication/information relevancy.

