## 2. Study Schema and objectives

[figure not shown]
Purpose:	To determine the effectiveness of risk communication for parents and students on students' attendance to school, COVID-19 testing and vaccine uptake
Design:	A clustered randomized controlled trial of risk communication intervention
Central Hypotheses:	Our central hypotheses are that students and parents who view the risk communications will be more likely to have less school absence, increased covid-19 testing and vaccine uptake.
Primary Objectives:	

• To determine if implementing three COVID-19 education comic books for children and two COVID-19 education videos for parents will lower school absenteeism, increase COVID-19 testing, and vaccine uptake in children.

Secondary Objectives:	

• To determine if implementing three COVID-19 education comics books for children and two COVID-19 education videos for parents will increase physical activity, improve sleep, increase emotional regulation in children.

• To determine if implementing three COVID-19 education comics books for children and two COVID-19 education videos for parents will increase physical activity, improve sleep, decrease depression and anxiety in parents

Population:	Children ages 5-13 enrolled in kindergarten to 5 th grade in Yakima School District
Study Size:	14 schools randomized; 7 to intervention and 7 to comparison arms with 450 children in each arm; a total of 900 children from 14 schools.
Primary Outcome Measurements:	

A. Attendance captured through the school district

B. COVID-19 testing data available through the school district testing program and self-reported survey

C. COVID-19 vaccine data available through self-reported survey

Study Duration:	2 years including enrollment period, 2 months to deliver the intervention, 5 months for post 1 survey, 7 months weeks for post 2 survey.

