### Study Timeline

## 4. Sample size and power

**For month 5 outcome.** We will enroll 900 elementary school students from 14 schools in the Yakima School District during the 2022-2023 school year. The sample size of 7 schools per study arm and an average of 50 students per school will provide 90% power to detect a difference of at least 4 hours per week ( $SD=8.0$ ) of in-person school attendance between the intervention and control groups, while assuming intra-cluster correlation (ICC) of 0.05 and type I error rate of 0.05. The estimated sample size of 14 schools with 900 students provides 80% power to detect a difference of 20% or more in COVID-19 vaccination rates between the two study arms, assuming ICC of 0.05 and type I error rate of 0.05.

Minimum detectable difference in hours per week between intervention arms in proposed cluster RCT assuming enrollment of 15 students per classroom, 80% power and two-sided type I error rate of 0.05.					
		Two Arm			
	Number of clusters per arm	30		40	
	ICC	.01	.10	.01	.10
Standard Deviation	5.0	1.0	1.5	.87	1.3
	7.5	1.5	2.2	1.3	1.9

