## 7. Outcome Definitions

### a. Primary Outcomes

The three co-primary outcomes for the trial are school absenteeism, COVID-19 testing, and COVID-19 vaccine uptake. Absenteeism are the student's school attendance data for 2022-2023 school year, COVID-19 data are captured through school testing and self-reported survey, and COVID-19 vaccine uptake data are captured through self-reported survey. All children and parent data after randomization will be included in the intention to treat analysis.

**Absenteeism:** total number of school days missed by each individual student participant, both for the entire school year and month-by-month, as captured and shared with us by school district administrative data systems. Absenteeism will also be measured by school days missed and will be a count variable.

**COVID-19 testing:** Health reports from the school are provided for the 2021-2022 and 2022-2023 school year that list positive covid test results of study participants with the date of testing and the school of attendance. Positive COVID test results will be a binary yes/no variable.

**COVID-19 vaccine uptake:** Parents are asked at enrollment to report their vaccination status and their child's vaccination status. At post survey 1 and post survey 2 the parent is asked to report if they or their child have received any COVID-19 vaccine or booster since enrollment. Vaccination status will be a binary yes/no variable.

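### The co-primary absence outcome has no single primary counting window, and a whole-year count may include days before any material was sent

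*SAP*

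**What the plan says.** **Attendance window.** SAP section 7.a defines absence as "total number of school days missed by each individual student participant, both for the entire school year and month-by-month", for 2022-2023. Protocol XIV gives the same two windows. Neither document says which is primary. SAP section 12.c.ii (and Protocol XI) rests the primary analysis on each student's mean weekly onsite hours over a study period with no dates. SAP section 4 opens its attendance power statement with "For month 5 outcome". The t-test and the zero-inflated negative binomial model in section 12.c.ii name no window and no offset for days enrolled.

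**Calendar.** SAP section 4 says "We will enroll 900 elementary school students from 14 schools in the Yakima School District during the 2022-2023 school year", and Protocol IV agrees. Protocol V (Risk Communication) sends materials monthly once enrolment has closed. Protocol XIII expects the study to run to June 2023. Protocol III, however, places the 14-school trial in 2021-2022. SAP section 2 gives "2 months to deliver the intervention, 5 months for post 1 survey, 7 months weeks for post 2 survey", while Protocol V puts the later assessments at months 4 and 6. Controls receive the materials at the end of the school year (Protocol III) or of the study (SAP section 3).

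**Limiting sentence.** SAP section 7.a adds: "All children and parent data after randomization will be included in the intention to treat analysis".

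**Other outcomes.** On testing: "Health reports from the school are provided for the 2021-2022 and 2022-2023 school year that list positive covid test results of study participants". The reports carry test dates, but the yes/no variable has no stated date limits. On vaccination: "Parents are asked at enrollment to report their vaccination status and their child's vaccination status". PROMIS T-scores are collected at baseline (SAP section 7.b). No model in section 12.c names a baseline covariate.

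**The concern.** A co-primary outcome needs one counting window fixed in advance. Here the whole year, the single months, the study period and month 5 all appear, and the choice could be made after the attendance data are seen.

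The whole-year window has a further problem if enrolment took place inside 2022-2023. Days before the first mailing contribute the same expected absences to both arms. The effect depends on the analysis:

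- In the count model, they move the rate ratio toward 1.
- In the t-test of totals, they leave the expected difference alone but add variance.

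Either way the trial becomes less sensitive to the effect it was designed to find.

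**Working it through.** **1. The plan's own power figure.** Inputs from SAP section 4: 7 schools per arm, 50 students per school, SD 8.0, ICC 0.05, type I error 0.05 (taken as two-sided), difference 4 h/week.

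- Design effect = 1 + 49 × 0.05 = 3.45
- Students per arm = 7 × 50 = 350
- SE = 8 × sqrt(2 × 3.45 / 350) = 1.123
- Noncentral t with 12 df: power = 90.4%, against a stated 90%

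The figure reproduces. It concerns weekly hours and uses no calendar dates, so it does not identify the window.

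**2. Share of the window after first distribution, f.** No date for first distribution appears in the text we worked from. Suppose follow-up of 6 months (Protocol V) or 7 months (SAP section 2) is counted from first distribution and ends in June 2023, and the school year is 9 or 10 months. Then f = 6/10 = 0.60, 6/9 = 0.67, 7/10 = 0.70 or 7/9 = 0.78. The documents do not say from which event the months are counted, so these are assumptions.

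**3. Rate ratio in the count model.** With no effect before distribution, full effect after it, and otherwise equal absence rates in the two parts of the year:

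observed RR = (1 − f) + f × true RR

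For an assumed true RR of 0.80:

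| f | Observed RR | Apparent reduction |
|---|---|---|
| 0.80 | 0.20 + 0.80 × 0.80 = 0.84 | 16% |
| 0.70 | 0.30 + 0.70 × 0.80 = 0.86 | 14% |
| 0.60 | 0.40 + 0.60 × 0.80 = 0.88 | 12% |

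**4. t-test of total days.** Assume a 10-month year, equal monthly variances and a common between-month correlation ρ. The variance of an n-month total is then proportional to n + n(n − 1)ρ. The ratio of the whole-year SD to the post-distribution SD is:

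- 2 months before distribution: sqrt(10/8) = 1.12 at ρ = 0, and 10/8 = 1.25 at ρ = 1
- 3 months before: sqrt(10/7) = 1.20, and 10/7 = 1.43

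The expected difference in days is unchanged, so the same difference is tested against a larger SD.

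**5. Hours average, worst case, for reference only.** If weekly hours were averaged over the whole school year, the difference would become 4f. With equal SDs of school means before and after distribution, correlated at r, the SE would be 1.123 × sqrt(f² + (1 − f)² + 2f(1 − f)r). At r = 1 the root equals 1, so holding the SD at 8 is the worst case. It gives power of 74%, 63% and 50% at f = 0.8, 0.7 and 0.6. At r = 0.3 to 0.7, power is 84.3-78.5%, 77.7-68.8% and 67.3-56.5%.

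**The case against.** **The dates may exist.** The Study Timeline heading just before SAP section 4 has no content in the text we worked from, and the schema in SAP section 2 and a figure in Protocol V are not shown. Enrolment and mailing dates may be there. This stands: we cannot say that the plan lacks them. A timeline would still not say which absence window is primary.

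**Section 7.a can be read as one whole-year total with a monthly breakdown.** That is a fair reading, and month 5 matches the first post survey, which does not supply attendance. But section 4 attaches month 5 to the attendance calculation, and section 12.c.ii uses a different period. The whole-year reading is also the one exposed to dilution.

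**The sentence on data after randomization may already limit the window.** It sets no start date for absences and does not override the whole-year definition. Even as a date limit, its effect is uncertain. Protocol V randomizes upon enrolment and, in the same section, once the study launches; mailing follows the close of enrolment. If schools were randomized when enrolment was complete, the gap to first mailing could be close to zero. The documents do not settle this.

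**The calendar is disputed.** If enrolment closed before 2022-2023 began, as Protocol III could imply, dilution would be small or absent. This stands.

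**Stronger readings.** A reader might infer that power falls from 90% to 50-74%. The documents do not support that: the whole-year window belongs to days missed, whereas hours are averaged over a study period that no passage equates with the school year, and those figures are the r = 1 extreme. Nor do they show that positive tests from 2021-2022 will count as outcomes; the randomization sentence may exclude them. Vaccination already has a start, because the follow-up surveys ask about doses since enrolment.

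**Intention to treat.** SAP section 8 fixes the arm in which each participant is analysed, not the calendar window. One common start date keeps every randomized child in the assigned arm.

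**Conclusion.** The missing primary window is established from the text and needs no assumption. Dilution is conditional on enrolment having run during 2022-2023 with mailing afterwards, which is the plain reading of Protocol IV, Protocol V and SAP section 4 but conflicts with Protocol III. Its size cannot be determined. The shift from 0.80 to 0.84-0.88 is an illustration that assumes f of 0.80 to 0.60, a true rate ratio of 0.80, similar absence rates across the year and full effect from the first mailing. No loss of power should be quoted as a finding.

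The lack of date limits on positive tests is a gap in wording. The absence of baseline covariates is a lost gain in precision, not a source of bias. The point warrants a change to the SAP; it does not invalidate the design.

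**What to change.** 1. **Primary attendance outcome.** Days missed from the first distribution date (the same calendar date in both arms) to the end of the school year or delayed delivery to controls, whichever comes first.
2. **Model.** Add an offset of log(days enrolled in that window) and, where the counted year has days before the start, the child's pre-start absence rate as a covariate.
3. **Supporting counts.** Keep whole-year and monthly absences as descriptive.
4. **Positive tests.** Count only those dated in the same window.
5. **Other models.** Adjust vaccination for status at enrolment and each PROMIS score for its baseline T-score.
6. **Alignment.** Make SAP sections 4, 7.a and 12.c.ii name the same period, with matching wording in Protocol XI and XIV. Reconcile the trial year in Protocol III with Protocol IV and SAP section 4, and state the dates of randomization and first distribution.

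**Cost.** Mostly SAP wording. Monthly absences, dated positive tests, enrolment vaccination status and baseline T-scores are already collected. The district must also supply enrolment and withdrawal dates, and absences by date if distribution began mid-month, under the data agreement in Protocol IX. The counting window becomes shorter. Parts of SAP sections 9 and 11 are in the past tense, so the change should be dated, with a statement of whether attendance by arm had been seen.

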## 3. Study Design

ROSSEY study is a cluster randomized controlled trial to test COVID-19 risk communication intervention with 900 participants from 14 elementary schools in the Yakima School District during

the 2022-2023 school year. Schools are randomized 1:1 (matched by school size and English language learners) to either intervention or control group. Students and parents randomized to the intervention group receive the COVID-19 risk communication intervention. Students and parents randomized to the control group receive the same risk communication intervention at the end of the study as a delayed intervention.

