### *Inferential Analyses:*

To determine if absenteeism differs between participants given COVID-19 educational material and the participants in the control group, we will conduct a complete-case analysis to compare mean absences between the intervention and control groups using a two-sample t-test.

We hypothesis implementing three COVID-19 education comic books for children and two COVID-19 education videos for parents will lower child's absenteeism and COVID infection rates and increased vaccine uptake.

School days missed will be modelled by a mixed zero inflated negative binomial model, with school specific random effects to account for clustering. COVID positive testing results will be modelled by a mixed logistic regression model, with school specific random effects to account for clustering.

Vaccine uptake will also be analyzed by mixed logistic regression model.

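### The COVID-19 testing co-primary is meant to show testing uptake, but the only testing variable the SAP defines and models is a positive result, which cannot show it

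*SAP*

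**What the plan says.** **The question is uptake.** The protocol Summary sets out to evaluate the effect of risk communication on testing uptake. Specific Aim 2 and the Aim 2 part of protocol section III call the outcome participation in testing. The SAP's primary objective (section 2) is that the materials "will lower school absenteeism, increase COVID-19 testing, and vaccine uptake in children". SAP section 7a names testing as one of three co-primary outcomes.

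**The variable is a positive result.** SAP section 2 gives the source as "COVID-19 testing data available through the school district testing program and self-reported survey". Under the testing heading, section 7a describes only district reports of positives: "Health reports from the school are provided for the 2021-2022 and 2022-2023 school year that list positive covid test results of study participants". It then defines one variable: "Positive COVID test results will be a binary yes/no variable".

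**The model and hypothesis concern infection.** SAP section 12c.ii states: "COVID positive testing results will be modelled by a mixed logistic regression model, with school specific random effects to account for clustering". The hypothesis beside it is that the materials will lower the child's "absenteeism and COVID infection rates and increased vaccine uptake". Testing uptake is not mentioned there.

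**The window is not fixed.** Section 7a says: "All children and parent data after randomization will be included in the intention to treat analysis". It also lists reports for 2021-2022, although SAP section 3 and the protocol's Sample Size section place the trial in 2022-2023 (protocol section III says 2021-2022). No end date is set, while SAP section 3 says: "Students and parents randomized to the control group receive the same risk communication intervention at the end of the study as a delayed intervention".

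**The concern.** A positive record needs two things: the child was tested, and the test was positive. A yes/no variable for a positive mixes the two and cannot separate them. The SAP also gives this variable two opposite directions of success. The section 2 objective implies more recorded positives, because more children test. The section 12c.ii hypothesis implies fewer.

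If the plan is followed exactly, an odds ratio above 1 may mean more testing or more infection, and one near 1 may hide a real rise in testing.

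Reading the variable as infection does not solve this. Testing at the district site is voluntary (protocol section V, testing procedures) and the materials promote it (section V, Risk Communication). If testing differs by arm, infection is detected unequally. The weekly encouragement to test and the gift cards are not restricted by arm, so they do not create such a difference by themselves.

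**Working it through.** **1. The plan's own figures.** SAP section 4 gives power for attendance and vaccination and none for testing, so there is no testing figure to reproduce. The attendance figure was used to choose the power method for step 5. Inputs are 7 schools per arm, 50 students per school, a 4-hour difference, SD 8.0, ICC 0.05 and alpha 0.05.
- Design effect = 1 + 49 × 0.05 = 3.45; effective n = 350 / 3.45 = 101.4 per arm.
- SE = 8 × √(2/101.4) = 1.123; 4 / 1.123 = 3.56.
- Noncentral t with 12 df (14 schools minus 2) gives power 90.4%, against the stated 90%.

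**2. The identity.** P(positive) = P(tested) × P(positive given tested). The point rests on this and needs no assumed rate. All rates below are assumptions, because the documents give none.

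**3. Same uptake gain, varying positivity among the tested.** Uptake is 30% control and 45% intervention, an uptake odds ratio of (0.45/0.55)/(0.30/0.70) = 1.91. Control positivity is 10%, so P(positive) in control is 0.30 × 0.10 = 0.030.

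| Positivity among tested, intervention vs control | P(positive), intervention | OR for a positive |
|---|---|---|
| unchanged | 0.45 × 0.10 = 0.045 | 1.52 |
| one third lower | 0.45 × 0.0667 = 0.030 | 1.00 |
| half | 0.45 × 0.05 = 0.0225 | 0.74 |

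At 5% control positivity the three odds ratios are 1.51, 1.00 and 0.75; at 20% they are 1.55, 1.00 and 0.74.

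At higher uptake, with 10% positivity unchanged:
- 60% to 75% (uptake OR 2.00): 0.060 vs 0.075, OR 1.27.
- 80% to 90% (uptake OR 2.25): 0.080 vs 0.090, OR 1.14.

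The fall in positivity that cancels the signal is 1 − (control uptake / intervention uptake): 33%, 20% and 11% for the three uptake pairs.

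**4. Same uptake gain, infection fixed.** Infection is 10% in both arms, every infected child who tests is positive, and there are no false positives. Overall uptake is again 30% vs 45%.

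| Share of infected children tested, control → intervention | P(positive) | OR | Share of non-infected children tested |
|---|---|---|---|
| 60% → 60% | 0.060 vs 0.060 | 1.00 | 26.7% → 43.3% |
| 60% → 65% | 0.060 vs 0.065 | 1.09 | 26.7% → 42.8% |
| 30% → 45% | 0.030 vs 0.045 | 1.52 | 30% → 45% |

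The signal depends on who the added testers are, not only on how many there are.

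**5. Power, for context only.** Inputs are 450 per arm and 900/14 = 64.3 per school. SE = √[(p0q0 + p1q1) × design effect / 450], with noncentral t on 12 df and matching ignored. Positives are taken at 5%, 10% and 20% positivity, equal in both arms. The documents give ICC 0.05 for attendance and vaccination only, so 0.01 is shown as well.

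| ICC | Design effect | Uptake 30% vs 45% | Positives at 5 / 10 / 20% |
|---|---|---|---|
| 0.05 | 1 + 63.3 × 0.05 = 4.16 | 56% | 7 / 8 / 12% |
| 0.01 | 1 + 63.3 × 0.01 = 1.63 | 92% | 9 / 14 / 23% |

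For uptake of 30% vs 50% at ICC 0.05, power is 80%. At ICC 0.05 with 6 df for a pair-level analysis and no gain from matching, the first row becomes 49% and 6 / 8 / 11%.

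**The case against.** The strongest reply is that the plan looks beyond positives. SAP sections 2 and 7a name self-report as a testing source, and section 5 lists the REDCap surveys among the sources for the primary analyses. Section 12c.i summarises testing results by count and percentage, separately from the district positives, and section 6 promises an odds ratio for binary outcomes. This shows that survey data may exist. It does not supply a definition of a tested child, a derived variable or a model, and an undefined descriptive summary cannot serve as a co-primary test.

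The window can also be defended. Section 7a restricts the analysis to data after randomisation and does not say that 2021-2022 positives enter the outcome. Protocol section III gives controls the materials at the close of the school year, so any overlap is probably confined to the end. That largely stands: the window is a point to settle, not evidence of contamination.

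The power comparison depends strongly on the assumed ICC and uptake gain, so it is context and not part of the argument.

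Finally, SAP section 12c.ii bases its primary analysis on onsite hours, and section 4 does not power testing. This limits the reach of the problem, but protocol section III and SAP section 7a still make testing a primary outcome.

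**Conclusion.** The concern holds and should be fixed before analysis. As written, the SAP specifies no analysis of the uptake question for this co-primary, and the variable it models cannot be read as uptake whatever the result. This follows from the definition alone.

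The size is illustrative and rests on assumed rates. A 15-point rise in uptake can appear as an odds ratio for a positive of 1.52, 1.00 or 0.74 depending on positivity among the tested. With infection equal in both arms, it can appear as 1.00, 1.09 or 1.52 depending on who the added testers are. The attendance and vaccination co-primaries are not affected.

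**What to change.** - **Outcome.** Define in SAP section 7a an uptake variable that counts tests of any result. Its form is for the sponsor: for example, at least one test, or the number or proportion of weeks tested, since weekly testing is encouraged.
- **Window.** Use the same period in both arms, from randomisation to before the delayed intervention. State how 2021-2022 reports are handled.
- **Source.** Name it. Use district records if negatives are supplied under the data use agreement (protocol section IX). Otherwise use the weekly check-in item on testing at the static site (section V), with a rule for missing weeks.
- **Model.** Use a mixed model with school random effects, as already planned.
- **Positives.** Report them as a separately named infection outcome with its own direction and a caveat on differential testing.
- **Fallback.** If neither source yields uptake, state that uptake cannot be assessed and rename the outcome as infection.

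The cost is SAP wording and one derived variable, from data the protocol plans to collect. Availability is not assured. SAP section 7a describes the school reports as listing positives only, the data use agreement lets the shared data change with district capacity, and the section III account of the weekly survey omits testing. If uptake rests on the survey, it is self-reported and limited to the static site, so non-response must be reported by arm. Power for uptake should be stated over a range of ICCs.
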